## **11.0 ADVERSE EVENT REPORTING**

### **11.1 Adverse Event Definitions**

- **Adverse Event**

An Adverse Event (AE) is any untoward medical occurrence in a clinical investigation subject administered a medicinal product; the event does not necessarily have a causal relationship with study drug administration or usage. An adverse event can therefore be any unfavorable and unintended sign (including an abnormal laboratory finding), symptom, or disease temporally associated with the use of a medicinal product, whether or not considered related to the medicinal product.

- **Serious Adverse Event**

A serious adverse event (SAE) is defined as an untoward medical occurrence that results in any of the following outcomes:

1. Death.
2. Life-threatening situation (i.e., with an immediate risk of death from the event as it occurred but not including an event that, had it occurred in a more serious form, might have caused death).
3. In-patient hospitalization or prolongation of existing hospitalization. Inpatient hospitalization comprises formal admission to a hospital for medical reasons, for any length of time, whether or not hospitalization extends overnight. However, hospital admissions for administration of the study drug, procedures required by the study protocol, or tumor-related diagnostic procedures are not considered serious.
4. Persistent or significant disability/incapacity or substantial disruption of the ability to conduct normal life functions.
5. Congenital anomaly/birth defect.
6. An important medical event that requires intervention to prevent one of the above outcomes.

- **Unexpected Adverse Event**

An unexpected adverse event is defined as an event that has a nature or severity, or frequency that is not consistent with the investigator brochure, protocol, or consent form. Please see section 11.6 for expected toxicities.

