### **11.5 Adverse Event Reporting Period**

All adverse events (grades 1-5) will be monitored and recorded in study-specific case report forms (CRFs) throughout the investigative phases of the study: from each T cell infusion through day 14 (for purposes of potential dose modification) and in conjunction with standard follow-up time points during the first year following T cell infusion. The detailed collection of AEs will stop at the time of commencement of new anti-tumor therapy.

AEs with an onset date prior to apheresis will not be recorded, except in the case of clinically significant worsening of the AE during the specified monitoring time frame. A subject withdrawn from the study because of an adverse event must be followed until the clinical outcome from the adverse event is determined.

The following events are *not* identified as AEs in this study:

- Disease progression or relapse.
- Hospitalization to facilitate infusions is not considered an AE. Any AE requiring prolongation of this hospitalization will be recorded and patient to applicable SAE reporting.
- Hospitalization to facilitate monitoring/due to the absence of caregiver/any other reason that is not related to T cells. Medical or surgical procedures in and of themselves, including those that

require hospitalization (e.g., surgery, endoscopy, biopsy procedures) are not considered AEs. However, an event or condition requiring such procedures may be an AE.

- Hospitalization that is otherwise unrelated to adverse events.

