#### **11.7.3 Institution-Sponsor Reporting Requirements**

The sponsor assumes responsibility for IND safety reporting to the FDA and participating investigators, in accordance with regulations under 21 CFR 312.32.

Each serious adverse event report received from the investigator will be evaluated by the Medical Monitor who will assess the seriousness of the event, the expectedness of the event, and the relationship to participation in the study. For regulatory reporting purposes, the IND Sponsor will determine expectedness relating to the investigational product using safety information specified in the Investigator Brochure. An event will be classified as related if either the investigator or the IND Sponsor determines that the event may be related to the study drug.

The IND Sponsor or designee will provide all investigators with a safety letter notifying them of an event that meets FDA IND Safety Reporting criteria. Investigators will be requested to provide written notification of safety report to the Fred Hutch IRB as soon as is practical, consistent with IRB requirements.

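### Section 11.5 says hospital admissions unrelated to T cells are not AEs, a causality test that contradicts the AE and SAE definitions in 11.1

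*Combined protocol and SAP*

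**What the plan says.** Section 11.1 defines an AE without a causal condition: "the event does not necessarily have a causal relationship with study drug administration or usage", and an unwanted sign, symptom or disease counts "whether or not considered related to the medicinal product". An event is serious if, among other outcomes, it results in "In-patient hospitalization or prolongation of existing hospitalization". Section 11.1 then takes out three kinds of stay: "hospital admissions for administration of the study drug, procedures required by the study protocol, or tumor-related diagnostic procedures are not considered serious". All three describe the purpose of the admission. None asks what caused it.

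Section 11.5 requires AEs of grades 1 to 5 to be recorded and then lists what is not "identified as AEs in this study". One item reads: "Hospitalization to facilitate monitoring/due to the absence of caregiver/any other reason that is not related to T cells". The same bullet goes on to exempt procedures as such, and adds that the condition behind a procedure may itself be an AE.

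Under 11.7.2 the serious or non-serious class sets the route to the IND Sponsor. All SAEs go within 2 business days, or 24 hours if fatal or life-threatening; non-serious events go through the CRF. Under 11.7.3 the Medical Monitor reviews each SAE report for seriousness, expectedness and relationship to study participation. Relatedness to the study product does not rest with the site alone: "An event will be classified as related if either the investigator or the IND Sponsor determines that the event may be related to the study".

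**The concern.** The regimen has more than one component. Section 10.8 names atezolizumab alongside T cells as active study treatment, and LD chemotherapy is scheduled where given (10.4, Appendix A). The 11.5 bullet asks only about T cells. An admission that the site puts down to LD chemotherapy, to atezolizumab or to an unrelated illness fits its literal wording, although 11.1 would count it.

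The order of steps matters too. In 11.7.3 relatedness is reviewed centrally, after a report arrives. The 11.5 bullet has the site settle relatedness to T cells earlier, when deciding whether the admission counts at all. If the admission is then disregarded, the Sponsor may have no SAE report on which to reach its own view. At stake is the expedited reporting of some events in a small trial of a new cell product given in combination.

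**Working it through.** The plan states no figure on this point, so the check is a comparison of text.

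**Step 1. Apply both sections to the same admissions.** Section 11.4 counts definite, probable and possible attributions as related, and unlikely or unrelated ones as not related.

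| Reason for admission | Section 11.1 | Literal reading of the 11.5 bullet |
|---|---|---|
| To give the T cells | Not serious (listed exception) | Excluded by a separate 11.5 bullet; no conflict |
| Observation or no caregiver, nothing medically wrong | No untoward occurrence, so no AE | Excluded; no conflict |
| Event at least possibly related to T cells | Serious | Not excluded; no conflict |
| Event attributed to LD chemotherapy or atezolizumab, rated unlikely or unrelated to T cells | Serious | Admission excluded; **conflict** |
| Intercurrent illness rated unrelated to T cells | Serious | Admission excluded; **conflict** |

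The two sections disagree in the last two rows only, and there the disagreement comes entirely from the T-cell limb of the bullet.

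**Step 2. Follow a conflicting case through reporting.** The event behind the admission still meets the 11.1 AE definition and is recorded. If the admission is not counted, and the event is not serious for another reason (fatal, life-threatening, disabling, or an important medical event), it is non-serious. It then goes to the CRF instead of to the Sponsor within 2 business days. The 11.7.3 review starts from SAE reports received, so that review is not triggered.

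**Step 3. Follow it to the DSMB.** Section 13.2 commits the DSMB to reviewing all toxicities of grade 3 or greater, and SAEs. A grade 3 or higher event is covered by its grade. A grade 1 or 2 event that led to admission falls under that commitment only as an SAE. Section 13.2 also refers in general terms to AE data, so such an event could miss review but need not.

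**Step 4. Look for text that closes the gap.**
- The sentence on prolonged stays in 11.5 covers only the infusion admission.
- The sentence on underlying conditions covers only those that need a procedure, and says only that they may be AEs.
- The last 11.5 bullet, on admissions otherwise unconnected with AEs, points to a narrower intent. But if the T-cell limb is taken at face value, that bullet adds almost nothing, so the site cannot tell which of the two governs.

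**Step 5. How firm is the site's attribution?** Under 11.4 both the possible and the unlikely category need two criteria. One event can meet two of each: plausible timing and a known pattern for possible; clinical state and another intervention for unlikely. So the same admission could be put on either side of the exclusion.

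**The case against.** The strongest reply is that the bullet removes the hospitalization and not the illness behind it. A toxicity of LD chemotherapy or atezolizumab remains an AE under 11.1, and 11.5 opens by requiring all grades to be recorded. The disputed words also close a list of logistical reasons, and the final bullet suggests that only admissions without an underlying AE were meant. On that reading nothing is lost. This is a fair account of the probable intent, and it limits the point to a risk in the wording. It does not remove the risk, because hospitalization can be the only thing that makes an event serious, and the bullet tells the site when a hospitalization does not count.

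Three stronger inferences are tempting, and the documents do not support them.

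- *The events disappear from the safety record.* They do not: AEs of all grades are recorded, and 13.2 has research data compared with the medical record.
- *Admissions to which T cells may have contributed are lost as well.* Under 11.4 even a possible link counts as related, so the exclusion does not reach them. What remains exposed is an event that the site rates unlikely or unrelated and that the Sponsor might have rated differently.
- *The dose-finding data are biased.* DLTs in 11.6 require at least a possible link to T cells. The toxicity that drives escalation in 12.2.1 is defined by grade, relatedness and expectedness. Neither depends on the serious label.

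**Conclusion.** The contradiction between 11.1 and 11.5 is in the current text and should be corrected. Its consequence is conditional. If the site applies the bullet literally, an AE whose only seriousness criterion is hospitalization, and which the site rates unrelated to T cells, could be handled as non-serious. It could then miss expedited reporting and Sponsor re-attribution and, below grade 3, the specified DSMB review.

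The size cannot be estimated from the documents. A reader might want to turn the 15 to 18 planned patients into a count of unreported SAEs. That would need an admission rate, the share attributed to causes other than T cells, the share serious for no other reason, and how often the bullet is read literally. None of these is given, and under the narrower reading the count is zero.

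The conclusion assumes that no other instruction settles the matter. The available text starts within section 10, so earlier sections could not be checked.

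**What to change.** In 11.5, delete the limb of the bullet that turns on relatedness to T cells. Limit the exclusion to admissions solely for monitoring, logistics or absence of a caregiver, with no underlying AE. Keep the procedures text that now runs on in the same bullet, preferably as a bullet of its own.

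Then add a sentence such as: *Within the AE reporting period, an AE that results in or prolongs hospitalization is reported as an SAE under 11.1 whatever its attribution (T cells, LD chemotherapy, bridging therapy, atezolizumab or another cause).* The three exceptions in 11.1 stay as they are. The time limit is needed because 11.5 stops detailed AE collection when new anti-tumor therapy starts, and 10.8 ends required collection when active treatment is discontinued.

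This is one edited bullet and one added sentence, and no treatment rule changes. The downside is a few more SAE reports to the Sponsor, some for events that prove unrelated.

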## **11.6 Dose-limiting Toxicities to Guide Dose Modification**

Dose-limiting toxicity (DLT) is defined as below and will be used to guide potential dose modification as detailed in **Sections 11.7.4 and 12.2.1**.

DLTs will be assessed for 14 days following the first infusion of the TCR-T cell product. The following events will be considered DLTs if they are attributed as at least possibly related to T cell administration. Grading will be done in accordance with the NCI Common Terminology Criteria for Adverse Events ([CTCAE Version 5.0](#) unless otherwise specified.

- Grade  $\geq$  3 allergic reaction related to the TCR-T cell infusion
- Grade  $\geq$  3 autoimmune reactions
- Any Grade 3 or 4 non-hematologic event that has not resolved to < grade 3 by day 28 post T cell infusion
- Grade  $\geq$  3 neurotoxicity of greater than 7 days duration
- Grade  $\geq$  3 neurotoxicity that does not revert to Grade 1 or baseline within 28 days
- Grade  $\geq$  3 seizures that do not resolve to < grade 3 within 3 days
- Grade  $\geq$  4 CRS (using criteria modified from Lee 2014)
- Grade 3 CRS that does not resolve to < grade 3 within 7 days
- Any other toxicity not meeting the above criteria that is deemed by the PI to represent a DLT

## **11.7 Adverse Event Reporting Requirements**

### **11.7.1 Reporting to IRB**

The investigator or designee must report events to the Fred Hutch IRB in accordance with the policies of the IRB.

### **11.7.2 Reporting to Sponsor**

The investigator or designee must report events to the drug or financial sponsor of the study as outlined in the contract.

Classification of an event as serious or non-serious determines the reporting procedures to be followed by the site for reporting the event to the IND Sponsor.

### **PI to IND Sponsor Reporting Requirements for Adverse Events**

Classification	Reporting Time	Reporting Action
----------------	----------------	------------------

Serious Adverse Event (SAE)	Fatal or life-threatening	Within 24 hours of research team awareness	Email notification to Sponsor
	All SAEs	Within 2 business days of research team* awareness	Email notification to Sponsor
Non-serious Adverse Event		Per CRF completion guidelines	Record information on appropriate CRFs

\*Research team is defined as the individuals listed on the delegation of authority log. Physicians listed on the study's delegation of authority log as attending physicians with delegated authority to administer informed consent will not be considered part of the research team unless additional responsibilities related to the conduct of the study have been delegated to them by the Principal Investigator.

#### **11.7.3 Institution-Sponsor Reporting Requirements**

The sponsor assumes responsibility for IND safety reporting to the FDA and participating investigators, in accordance with regulations under 21 CFR 312.32.

Each serious adverse event report received from the investigator will be evaluated by the Medical Monitor who will assess the seriousness of the event, the expectedness of the event, and the relationship to participation in the study. For regulatory reporting purposes, the IND Sponsor will determine expectedness relating to the investigational product using safety information specified in the Investigator Brochure. An event will be classified as related if either the investigator or the IND Sponsor determines that the event may be related to the study drug.

The IND Sponsor or designee will provide all investigators with a safety letter notifying them of an event that meets FDA IND Safety Reporting criteria. Investigators will be requested to provide written notification of safety report to the Fred Hutch IRB as soon as is practical, consistent with IRB requirements.

#### **11.7.4 Dose Assessment Committee**

Because this is a Phase 1 dose finding study of a cellular therapy where both efficacy and toxicity may be observed in non-dose dependent manners, a Dose Assessment Committee (DAC) is established. The DAC charter is available in **Appendix H**. The DAC will work in an advisory capacity to the PI throughout the trial, as needed. The decision to escalate/de-escalate will be made in consultation with the DAC. The PI and IND Sponsor may override the algorithm's allocation of a patient to a particular dose level or schedule.

The IIRC Clinical Operations team will collect, abstract, and present adverse events to the PI and he will attribute. Treatment of patients in the dose-escalation/de-escalation groups will be staggered such that a minimum of a 28-day interval following infusion is required between each set of 3 or 4 patients before escalating to the next dose level, and 14 days between patients within the same dose level. Within 10 business days of Day 28 of at least the prior 3 or 4 patients, data will be presented and reviewed by the DAC.

## 12.0 STATISTICAL CONSIDERATIONS

### 12.1 Type of Study

Our study is a phase I/II, non-blinded interventional trial. Our target sample size is 15-18 patients (8-12 per year/1.5-2 years). This enrollment target is chosen for three reasons: it is achievable from an enrollment standpoint (our clinic sees hundreds of metastatic TNBC, urothelial or NSCLC patients potentially eligible per year), it is logistically possible from a funding and cell processing facility standpoint, and it allows >80% power to observe a statistically significant (at one-sided 0.05 level) efficacy signal that is clinically meaningful (see below). Patients will be treated at three potential dose levels (from  $1 \times 10^9$  up to  $5 \times 10^9$  TCR-MagIC transgenic CD3+).

### 12.2 Safety Assessment

#### 12.2.1 Guidelines for Dose Modification

The treatment will be considered to have an acceptable safety profile if the observed DLT rate is consistent with a true rate that does not exceed 35%, and this rate will be used as a guide for decisions related to potential dose modification.

The initial dose level 1 patients will be treated and followed for toxicity for 14 days. Subsequent patients within this group will be able to receive their T cell infusion within 28 days of the last patient receiving their first T cell infusion. Per DAC general guidelines but pending their final recommendation, if zero of the first three dose level 1 patients' experiences treatment-related and unexpected grade  $\geq 3$  toxicity, escalation will proceed to the next dose level. If one patient experiences a treatment-related and unexpected grade  $\geq 3$  toxicity, 3 additional patients will be recruited at the first dose level. If no additional patients experience treatment-related and unexpected grade  $\geq 3$  toxicity, escalation to the next dose level will take place. If 2 or more patients at the first dose level experience treatment-related and unexpected grade  $\geq 3$  toxicity, at the point that the two toxicities occur, the trial will be suspended and, after a detailed review of the potential causes of toxicity, the DAC may consider recommending changing the cell dose pending DSMB review. If any of the dose level 1 patients experience treatment related death, the trial will be suspended and, after a detailed review of the potential causes of toxicity, consideration given to changing the cell dose or construct pending DSMB review. If the DSMB deems safe to re-initiate the protocol, de-escalation will take place (Figure 6) for the second cohort.

If at any point any patient experiences grade 3 or higher unexpected treatment-related toxicity, that particular patient will no longer receive T cell infusions, atezolizumab or other study related active therapies. They will continue to be followed for response and outcome.

By determination of the DAC and attributed to cellular therapy, evidence of excessive toxicity will be an observed proportion of toxicities for which the associated lower 80% confidence limit exceeds 40%. Operationally, this limit will be met if any of the following proportions is observed: 2/2, 3/3-4, 4/5-6, 5/7-8, 6/9-10, 7/11-12, 8/13-14, 9/15. Under these rules, if the true probability of toxicity is 20%, the probability of suspension is approximately 0.06. If the true probability of toxicity is 60%, the probability of suspension is approximately 0.84 (based on 5,000 simulations).

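### The dose level 1 steps count only related, unexpected grade ≥3 toxicity, so a DLT classed as expected adds nothing to the count

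*Combined protocol and SAP*

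**What the plan says.** - **Section 11.6, purpose:** "Dose-limiting toxicity (DLT) is defined as below and will be used to guide potential dose modification as detailed in" Sections 11.7.4 and 12.2.1.
- **Section 11.6, attribution:** "The following events will be considered DLTs if they are attributed as at least possibly related to T cell administration". The list sets type, grade and duration limits. It sets no condition on whether the event was expected. Its last item is discretionary: "Any other toxicity not meeting the above criteria that is deemed by the PI to represent a DLT".
- **Section 12.2.1, guide:** the treatment has an "acceptable safety profile if the observed DLT rate is consistent with a true rate that does not exceed 35" per cent, and that rate guides dose modification.
- **Section 12.2.1, steps:** these are introduced with "Per DAC general guidelines but pending their final recommendation". Zero of three leads to escalation. Then: "If one patient experiences a treatment-related and unexpected grade" 3 or higher toxicity, three more patients are treated, and escalation follows if none of them has one. Two or more suspend the trial. Every count uses this related-and-unexpected event, and none mentions DLTs. A treatment-related death suspends the trial separately.
- **Section 12.2.1, excessive-toxicity boundary:** 2/2, 3/3-4, 4/5-6 and so on to 9/15. It counts toxicities attributed to cellular therapy, has no expectedness condition, and is not tied to the 11.6 list.
- **Section 11.1:** an event is unexpected if its nature, severity or frequency does not fit the brochure, protocol or consent form. The reader is sent to 11.6 for expected toxicities, but 11.6 is the DLT list.

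**The concern.** The section sets its guide in terms of one event and writes its escalation count in terms of another. Nothing in the text equates the two. Section 11.6 already spares tolerable toxicity through its duration limits; its general item, for example, covers a grade 3 or 4 "non-hematologic event that has not resolved to" below grade 3 by day 28. An expectedness filter on top of that removes events which 11.6 kept as dose-limiting.

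What is at stake is the decision to raise the cell dose after the first cohort. Two patients out of three could have DLTs while the written count stands at 0/3, for which the stated step is escalation.

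**Working it through.** **1. The plan's own figures.** For the boundary, the plan gives suspension probabilities of about 0.06 and 0.84 at true toxicity rates of 20% and 60%. An exact recursion that checks the boundary after each patient up to 15 gives 0.062 and 0.824, within 0.02 of both. These figures describe the boundary. The plan gives no such figure for the dose level 1 steps.

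**2. Does the boundary catch what the steps miss?** It fits one-sided 80% exact lower limits above 0.40. For 2/2 the limit is 0.447, so the trial stops. For 2/3 it is 0.287, so it does not. Even if the boundary counts all DLTs, it stops 2 in 3 only when both fall in the first two patients. Likewise 3/6 (limit 0.269) passes, so one counted DLT plus two expected ones in six patients can also escalate.

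**3. Steps if DLTs are counted.** With per-patient probability q, P(escalate) = (1−q)³ + 3q(1−q)⁵. At q = 0.35 this is 0.2746 + 0.1218 = 0.396. Escalation then allows at most one DLT, so P(escalate with ≥2 DLTs) = 0.

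**4. Steps as written.** The true DLT rate is p = 0.35, the plan's guide. The documents do not give the following shares, so all are assumptions:
- d: share of DLTs classed as expected
- s: share of patients without a DLT who have another counted event
- e: the same share among patients whose DLT is expected (either e = s or e = 0)

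Each patient is one of four types:
- counted DLT: a = p(1−d) + pde
- uncounted DLT: u = pd(1−e)
- counted non-DLT: c = (1−p)s
- neither: z = (1−p)(1−s)

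The steps are taken as followed, the boundary is applied to all DLTs, and the death rule is not modelled. Listing the patient orders that survive both rules gives

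P(escalate with ≥2 DLTs) = 2u²z + (3az² + 6cuz)(3uz² + 3u²z) + (4auz + 2cu²)·z(z² + 2uz) + 3cz²(3u²z + u³).

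The first term is escalation on a count of 0/3; the rest is escalation after six patients.

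Example with d = 0.5 and s = 0, so a = u = 0.175, c = 0, z = 0.65:
- first term: 2 × 0.0306 × 0.65 = 0.0398
- second: 0.2218 × 0.2815 = 0.0624
- third: 0.0796 × 0.4225 = 0.0336
- total: 0.136

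Results at p = 0.35 (two values where e = s and e = 0 differ after rounding):

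| d | s | P(escalate) | P(escalate with ≥2 DLTs) |
|---|---|---|---|
| 0 | 0 | 0.40 | 0 |
| 10% | 0 | 0.46 | 0.03 |
| 10% | 5% | 0.39–0.40 | 0.02 |
| 10% | 20% | 0.23–0.24 | 0.01 |
| 25% | 10% | 0.41–0.42 | 0.05 |
| 50% | 0 | 0.69 | 0.14 |
| 50% | 20% | 0.38–0.44 | 0.07–0.09 |
| 75% | 0 | 0.81 | 0.17 |
| 75% | 20% | 0.49–0.58 | 0.12–0.16 |

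**5. Opposite direction.** At a 20% DLT rate with no DLT excluded and s = 20%, q = 0.20 + 0.80 × 0.20 = 0.36. P(escalate) is then 0.2621 + 0.1160 = 0.378, against 0.709 if only DLTs count.

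**The case against.** **The steps do not bind.** They await the DAC's recommendation. Section 11.7.4 has escalation decided in consultation with the DAC after Day 28 data, with PI and sponsor override. Section 13.2 has the DSMB review all grade 3 or greater toxicities, and a treatment-related death suspends the trial whatever its expectedness. This stands as mitigation. It does not change the written count, and the DAC is advisory and made up of investigators directly involved in the study (Appendix H).

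**Section 11.1 limits the problem.** Two grade 4 CRS events in three patients may well be unexpected by severity or frequency, and would then count. A constant d ignores this, so the larger figures in the table lean high. This stands as well.

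**Counting unexpected non-DLT events is cautious.** A reader might infer that suspending after two unexpected, related grade 3 events that resolve quickly is a second error. It is not: such events could signal off-target toxicity, suspension leads to review, and the PI may deem them DLTs anyway. Replacing the counted event with DLTs alone would drop these events and could delay some suspensions to day 28.

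**The 11.1 pointer.** Read literally, it might suggest that every listed DLT is expected. It is more likely a stale cross-reference and carries no weight here.

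**Conclusion.** The mismatch stands on the text: expectedness can remove a DLT from the dose level 1 count, and the boundary is not a full backstop, since 2/3 passes unless both DLTs come first and its event is undefined.

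A reader might infer that the rule is therefore biased towards escalation. The documents do not support that. Excluding DLTs raises P(escalate) and counting other events lowers it; modest shares (10% with 5%, or 25% with 10%) leave it at 0.39 to 0.42, against 0.40. Net direction and size are undetermined, because no expected share is given. The text available for review starts within Section 10 and does not show Figure 6, so a list of expected toxicities may exist elsewhere.

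What can be said is narrower. At a 35% DLT rate, P(escalate despite two or more DLTs) is 0 if DLTs are counted and about 0.01 to 0.17 over the assumed shares. This should be fixed: confidence is high on the wording and low on any one figure.

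**What to change.** In each dose level 1 step of Section 12.2.1, count a DLT as defined in 11.6, or any other treatment-related, unexpected toxicity of grade 3 or higher. Expectedness can then add events but never exclude a DLT. State which event the excessive-toxicity boundary counts, at minimum all 11.6 DLTs. Correct the 11.1 pointer as an editorial matter.

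The cost is protocol wording and somewhat stricter escalation. At a 35% DLT rate, if 10% of non-DLT patients have another counted event (assumed), q = 0.35 + 0.65 × 0.10 = 0.415 and P(escalate) = 0.2002 + 0.0853 = 0.29. At 20%, q = 0.48 and P(escalate) = 0.1406 + 0.0547 = 0.20. Both compare with 0.40 for DLTs alone. DLT items that depend on day 28 are known by the DAC review already planned after Day 28, and unexpected events still count when they occur.

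### Section 12.2.1 makes suspension after a treatment-related death mandatory only at dose level 1; at the other planned levels the decision to pause is discretionary

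*Combined protocol and SAP*

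**What the plan says.** Section 12.1 of the combined protocol and SAP states: "Patients will be treated at three potential dose levels".

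Section 12.2.1 contains these suspension and stopping rules:

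- **Death.** "If any of the dose level 1 patients experience treatment related death, the trial will be suspended". A review of causes follows, and a change of cell dose or construct is considered pending DSMB review. If the DSMB allows a restart, "de-escalation will take place (Figure 6) for the second cohort".
- **Two events.** The sentence before it has the same scope: "If 2 or more patients at the first dose level experience treatment-related and unexpected grade" 3 or higher toxicity, the trial is suspended.
- **Any patient.** After an unexpected related toxicity of grade 3 or higher, at any point in the trial, "that particular patient will no longer receive T cell infusions, atezolizumab or other study related active therapies". This rule acts on the patient, not on the trial.
- **Excessive toxicity.** This rule is not tied to a dose level. It is met at "2/2, 3/3-4, 4/5-6, 5/7-8, 6/9-10, 7/11-12, 8/13-14, 9/15".

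Other sections apply at every level. Under 11.7.2, fatal or life-threatening SAEs go to the sponsor within 24 hours of awareness. Under 11.7.3, the Medical Monitor evaluates each SAE report. Under 13.2, SAEs are reviewed when they occur, the study team meets at least monthly on adverse events and stopping rules, and the DSMB meets once a dose level has been treated, or earlier on request. Section 11.7.4 sets 14 days between patients within a level and a DAC data review within 10 business days of Day 28 of the prior 3 or 4 patients. Under section 15.0, the PI or sponsor may terminate at any time.

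**The concern.** The death rule protects the patients next in line: no one else is infused until the cause has been examined. As worded, it covers only the first level. A related death at a higher cell dose would not trigger it. Nor would a second related death, in the de-escalated cohort that may follow a dose level 1 death. Section 11.7.4 itself says that toxicity of a cellular therapy may not depend on dose, so there is no evident reason to confine the automatic pause to one level.

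At stake is whether the next infusion is held by rule or only if someone decides to hold it. The two reviews that guide dose decisions, by the DAC and the DSMB, are scheduled after a set or level has been treated. They could therefore come after further patients have been infused.

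**Working it through.** **1. Can one death meet the excessive-toxicity list?**

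Inputs from 12.2.1: the rule is a lower 80% confidence limit above 40%, with the listed boundaries. The exact one-sided lower limit for k events in n patients is the 0.20 quantile of Beta(k, n - k + 1). It reproduces all 14 listed boundaries from n = 2 to n = 15.

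| Events / patients | Lower 80% limit | Above 0.40? |
|---|---|---|
| 1/1 | 0.200 | no |
| 1/2 | 0.106 | no |
| 1/4 | 0.054 | no |
| 2/2 | 0.447 | yes |

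A single event never meets the list at any n.

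**2. Is the list counted by level or across the trial?**

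The plan's own figures are the check. It states that "if the true probability of toxicity is 20%, the probability of suspension is approximately 0.06", and about 0.84 if the true probability is 60%. I computed the exact probability of crossing the boundary, checking after each patient.

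| Counting basis | True rate 20% | True rate 60% |
|---|---|---|
| Stated in 12.2.1 | 0.06 | 0.84 |
| One running count, n = 15 | 0.062 | 0.824 |
| One running count, n = 16 (boundary extended to 9/16) | 0.062 | 0.847 |
| Separate counts, three levels of 5 or 6 patients | 0.150-0.164 | 0.898-0.952 |

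The separate-count row is 1 - (1 - s)^3, where s is the crossing probability within one level. For 5 patients s is 0.0528 at 20%, giving 1 - 0.9472^3 = 0.150. The stated figures fit one running count.

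On that basis the list reacts later at higher levels, even if every patient there has an event:

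- After 0/3 at dose level 1, the results 1/4, 2/5, 3/6 and 4/7 (limit 0.350) do not meet it. It is first met at 5/8 (0.416).
- If dose level 1 was expanded ("3 additional patients will be recruited at the first dose level") and ended at 1/6, 6/11 (0.378) does not meet it and 7/12 (0.422) does.

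Either way, the list does not stand in for a one-death rule.

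**3. How many infusions could precede the scheduled DAC review?**

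Inputs from 11.7.4: 14-day spacing, sets of 3 or 4, and review within 10 business days (about 14 calendar days) of Day 28. Assume that the first patient of the set dies of a related event and nobody calls a hold.

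| Set | Infusion days | Day 28 of last patient | Review due by about | Further infusions |
|---|---|---|---|---|
| 3 | 0, 14, 28 | 28 + 28 = 56 | 56 + 14 = day 70 | up to 2 |
| 4 | 0, 14, 28, 42 | 42 + 28 = 70 | 70 + 14 = day 84 | up to 3 |

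**4. How realistic is that spacing?**

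Section 12.1 plans 8-12 patients per year, which averages 365/12 = 30 to 365/8 = 46 days between patients. At that pace a monthly team review would usually come before the next infusion. The maximum counts are unchanged, but reaching them would mean that everyone who saw the death chose not to act.

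**The case against.** The strongest objection is that the paragraph may only walk through the first cohort. It opens with the initial dose level 1 patients and ends with the second cohort, and every cohort rule in it names the first level. Read equally literally, it would also lack a rule for escalating from level 2 to level 3. Rules for later levels may sit in Figure 6, the DSMB charter or sections before 10. None of these is in the text available for review, and their absence here is not a fault of the plan. This stands, and it limits the point to the scope of 12.2.1 as worded.

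A second objection is that much of the response to a death is mandatory at every level: the 24-hour report, the Medical Monitor's evaluation, review on occurrence and the monthly review. This also stands. But reporting and review are not suspension. The same safeguards apply at dose level 1, where the plan still chose to add an automatic pause.

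A reader might infer that higher levels have no stopping rule, or that infusions would simply continue after a death. The documents support neither. The excessive-toxicity list is not limited to a level, ad hoc DSMB meetings are possible, and the PI or sponsor can stop the trial at any time. A real death would probably lead to a hold. What is missing from the text reviewed is only the requirement to pause.

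**Conclusion.** The point holds as a gap in the wording of 12.2.1. In the text available, a treatment-related death forces suspension only at dose level 1. Elsewhere the event must be reported and reviewed, but the pause is discretionary, and one event cannot trigger the excessive-toxicity rule.

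The size is at most 2 or 3 further infusions before the scheduled DAC review. That rests on a death in the first patient of a set, the minimum 14-day spacing and no discretionary hold. It is a worst case, not a forecast.

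It would be too strong to conclude that the protocol as a whole lacks the rule, since the unseen figure, charter and earlier sections may contain it. Confidence is therefore medium, and the label is a cheap improvement.

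**What to change.** In 12.2.1:

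1. Change the death sentence so that it applies to any patient at any dose level, not only to those at dose level 1.
2. Change the restart sentence so that any de-escalation after DSMB clearance is from the level at which the death occurred. As worded it refers only to the second cohort, which would not fit a death at level 2 or 3.
3. If Figure 6, the DSMB charter or an earlier section already has this rule, align 12.2.1 with it.

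The cost is an edit to two sentences. The downside is a possible temporary pause after one related death at another level, which the plan already accepts at dose level 1.
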